1.1 Study rationale

1.1.1 Benefit and risk assessment

This is a study without an intervention (e.g. novel drug administration) which makes the risk of injuries or side effect from drug administration none. Taking blood samples can be an unpleasant procedure and can lead to bruises. The CSF sampling could be an uncomfortable procedure and may lead to side effects, for instance post-dural puncture headache or bruising.

There is no benefit for the subjects who participate in the study. This study increases the knowledge about possible relationships between different types of blood plasma biomarkers in this specific cohort of elderly. The study may yield an algorithm (base on e.g. the NeuroCart results, CSF information and plasma based biomarkers from the subjects) that can be used to predict the likelihood that an otherwise healthy subject has AD pathology before clinical disease onset. This may lead to fewer lumbar punctures in future studies aimed at finding subjects to participate in clinical trials with drugs aiming at slowing AD disease onset. Subjects of this current study may be asked to participate in future studies.

1.1.2 Medical and regulatory background

Not applicable.

1.1.3 Study population

For this study a population of healthy elderly subjects aged 65 years and over has been chosen as the prevalence of geriatric cognitive disorders such as AD is increasing from approximately this age onwards.

1.1.4 Sample Size Justification

This is an exploratory study, therefore the samples size is not based on statistical considerations. The aim for this study is to enroll 200 subjects. The assays to determine $A\beta$ from CSF are well established methods and the sample size justification for this current study is therefore based on previous research on amyloid pathology in CSF. In this study we select elderly at the age of 65 and higher of which at least a hundred will be above the age of 70. According to Jansen et al., (2015) we can expect at least 19% amyloid pathology in a 65+ population and 23% amyloid pathology among cognitively healthy 70+ elderly subjects. As we expect more responsiveness for study participation from elderly between the age of 65 till 70, based on our experience with previous studies in this age range, at least 100 subjects of >70 years old will be included in this study to be able to differentiate between age, which results in approximately 23 A β positive subjects versus approximately 77 A β negative subjects in this elderly age group. Along with approximately 19 A β positive subjects versus approximately 81 A β negative subjects in the age group 65-70 we expect to find at least 42 A β positive healthy elderly subjects. Based on previous comparable studies, these numbers are considered appropriate for a correlational study aimed at defining an algorithm [22, 23].

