This is an exploratory study, therefore the samples size is not based on statistical considerations. The aim for this study is to enroll 200 subjects. The assays to determine A β from CSF are well established methods and the sample size justification for this current study is therefore based on previous research on amyloid pathology in CSF. In this study we select elderly at the age of 65 and higher of which at least a hundred will be above the age of 70. According to Jansen et al., (2015) we can expect at least 19% amyloid pathology in a 65+ population and 23% amyloid pathology among cognitively healthy 70+ elderly subjects. As we expect more responsiveness for study participation from elderly between the age of 65 till 70, based on our experience with previous studies in this age range, at least 100 subjects of >70 years old will be included in this study to be able to differentiate between age, which results in approximately 23 A β positive subjects versus approximately 77 A β negative subjects in this elderly age group. Along with approximately 19 A β positive subjects versus approximately 81 A β negative subjects in the age group 65-70 we expect to find at least 42 A β positive healthy elderly subjects. Based on previous comparable studies, these numbers are considered appropriate for a correlational study aimed at defining an algorithm [22, 23].

Inclusion criteria

1. Males and females, aged 65 and older (inclusive);

- 2. Willing and able to perform the cognitive tests, as evidenced by performance on the training session of the cognitive tests;
- 3. Willing and able to give written informed consent and to comply with the study procedures.

Exclusion criteria

- 1. Legal incapacity or inability to understand or comply with the requirements of the study;
- Evidence of cognitive deterioration, as indicated by a diagnosis of a cognitive disorder (including but not limited to MCI, Alzheimer's disease, Lewy Body Dementia, Frontotemporal Dementia);
- 3. History or symptoms of significant psychiatric disease in the past 3 years (including but not limited to clinical depression, schizophrenia);
- 4. A Mini Mental State Examination (MMSE) score of ≤24;
- 5. A Geriatric Depression Scale 15 (GDS) score of ≥6;
- 6. Presence of drug abuse, or positive urine drug screen (UDS) at screening or occasion;

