4.2 Inclusion criteria

- 1. Males and females, aged 65 and older (inclusive);
- 2. Willing and able to perform the cognitive tests, as evidenced by performance on the training session of the cognitive tests;
- 3. Willing and able to give written informed consent.

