9.6 Subject disposition

Subject disposition will be listed by subject.

The following subject data will be summarized:

- Number and percentage of subjects screened,
- Number and percentage of subjects enrolled,
- Number and percentage of subjects included in the PD analysis population.
- Number and percentage of subjects completed,

A subject who completed the study is defined as a subject where the 4 hour biomarker plasma sample was assessed.

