10.7 End of study report

The investigator will notify the EC of the end of the study within a period of 8 weeks. The end of the study is when 200 subjects have had their study visit.

In case the study is ended prematurely, the investigator will notify the EC, including the reasons for the premature termination.

Within one year after the end of the study, the investigator will submit a final study report with the results of the study, including any publications/abstracts of the study, to the EC. The principal investigator will be the signatories for the study report.

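### The count of Aβ-positive subjects that supports N=200 is an expected value worded as a minimum, rests on a 19% rate whose age group is unclear, and is not tied to subjects with a CSF result

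*Protocol*

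**What the plan says.** Section 1.1.4 (repeated in the synopsis) declares that N has no statistical basis, and section 9.3 agrees. "The aim for this study is to enroll 200 subjects", and "at least 100 subjects of >70 years old will be included in this study". The support offered is an expected number of positives. The rates come from a cited meta-analysis: "we can expect at least 19% amyloid pathology in a 65+ population and 23% amyloid pathology among cognitively healthy 70+ elderly subjects". Taking 100 subjects per age group, the section obtains about 23 positives above 70 and about 19 at ages 65-70, and concludes: "in the age group 65-70 we expect to find at least 42".

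The outcome of the main objective is the CSF Aβ 1-42 class (sections 2 and 4.4). The rules that count subjects are these:

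- **Enrolment (4.1):** at least 200 subjects who pass screening.
- **Inclusion criterion 3:** in section 4.2, "Willing and able to give written informed consent"; in the synopsis, "Willing and able to give written informed consent and to comply with the study procedures".
- **Lumbar puncture consent (4.4):** requested from subjects, but not a listed inclusion criterion.
- **Replacement (4.8.2):** withdrawals only, at the investigator's discretion.
- **Completion (9.6):** "A subject who completed the study is defined as a subject where the 4 hour biomarker plasma sample was assessed".
- **End of study (10.7):** "The end of the study is when 200 subjects have had their study visit".

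**The concern.** Three features of the 42 need attention. First, it adds two expected counts, each given as approximate, and words the total as a minimum. Second, the 19% is introduced for everyone aged 65 and over but applied only to ages 65-70, beside a separate 23% for the over-70s. Third, the 42 assumes a CSF class for all 200 subjects, while the counting rules refer to screening, visits and a plasma sample.

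This matters because the number of positives is the only quantitative support for N=200. It also limits how much the LASSO model can learn: section 9.8.1 already expects few events per variable. A reader who takes 42 as a minimum will be too confident in the events available.

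**Working it through.** **Inputs from the protocol.** 100 subjects above 70 and 100 aged 65-70; rates of 23% and 19% (section 1.1.4). **Not in the protocol, so assumed:** the share of the 65+ source population aged 65-70 (w), taken as 30% to 70%; the proportion without a CSF result, taken as 5% or 10%.

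**1. The plan's own figure.** 100 × 0.23 + 100 × 0.19 = 23 + 19 = 42. It reproduces.

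**2. Is 42 a minimum?** Treat the total as the sum of two independent binomials, Bin(100, 0.23) + Bin(100, 0.19).
- Variance: 100 × 0.23 × 0.77 + 100 × 0.19 × 0.81 = 17.71 + 15.39 = 33.10, so SD = 5.75.
- Exact convolution: P(42 or more) = 0.528; 95% range 31 to 54.

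Enrolling more over-70s changes little: 120 of 200 gives 120 × 0.23 + 80 × 0.19 = 42.8, and 140 gives 140 × 0.23 + 60 × 0.19 = 43.6.

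**3. If 19% is the pooled 65+ rate.** Then 0.19 = w × p + (1 − w) × 0.23, where p is the 65-70 rate. So p = [0.19 − (1 − w) × 0.23] / w, and the expected total is 23 + 100p.

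| Share aged 65-70 (assumed) | Implied 65-70 rate | Expected positives in 100 + 100 |
|---|---|---|
| 30% | 9.7% | 32.7 |
| 50% | 15.0% | 38.0 |
| 70% | 17.3% | 40.3 |

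At the even split, Bin(100, 0.23) + Bin(100, 0.15) gives P(42 or more) = 0.26 and a 95% range of 27 to 49.

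**4. Subjects without a CSF result.** Section 9.4 does not impute missing results, so such a subject has no outcome class. Losses are assumed equal in both age groups.

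| Without CSF (assumed) | N with CSF | Expected at 19%/23% | P(42 or more) | Expected at 15%/23% | P(42 or more) |
|---|---|---|---|---|---|
| 0% | 200 | 42.0 | 0.53 | 38.0 | 0.26 |
| 5% | 190 | 39.9 | 0.38 | 36.1 | 0.16 |
| 10% | 180 | 37.8 | 0.25 | 34.2 | 0.08 |

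The two right-hand columns combine two assumptions: the even age split and the loss rate.

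**The case against.** The strongest reply concerns the 19%. Section 1.1.4 qualifies it as a lower bound. If 19% holds at 65-70 and 23% above 70, the overall 65+ rate lies between the two (21% at an even split), which satisfies that bound. On this reading the stated rates do not contradict 42. The background text, which says that only 19% of this population will be abnormal and adds that the figure rises with age from 65, points towards a pooled rate but does not settle it. The cited source is not at hand. This stands: a reader might infer that the protocol's arithmetic is wrong, or that the correct total is 38, and the document supports neither. The sum is right, and 38 needs both a pooled 19% and an even age split that the protocol never gives.

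A reader might also infer that nothing links the 200 to the lumbar puncture. That goes too far. The synopsis rationale describes the 200 as willing to undergo it, and the 1000 to be approached follow from 20% acceptance (200 / 0.20). Section 4.3 excludes contraindications to the procedure and inability to comply with study requirements. Table 1 schedules CSF sampling within the visit.

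Nor would losses necessarily pass unseen. Section 9.2 makes missing evaluations for relevant endpoints a deviation category. Section 9.5 admits only data that can contribute to the objectives. Section 9.6 governs disposition reporting, not the model's denominator. All of that stands. Even so, willingness and fitness for the procedure are not the same as an evaluable result, and no counting rule requires one.

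Finally, N is declared non-statistical, so no power figure changes. That limits the size of the point but does not make a mean into a minimum.

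**Conclusion.** The point holds in this limited form. The wording as a minimum is wrong on either reading of the 19%: at the rates most favourable to the plan, reaching 42 is close to an even chance (53%). That result assumes independent subjects, 100 per age group and a CSF result for all 200.

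The age group of the 19% is unclear. If it is the pooled rate, the expectation falls to about 33 to 40 for 65-70 shares of 30% to 70%; at the even split the shortfall is 4 positives, about 10%. Which reading is right cannot be decided from the protocol.

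The link to lumbar puncture exists in the rationale but stops short of an obtained CSF Aβ 1-42 result in sections 4.1, 9.6 and 10.7. The loss rates above are illustrative. The effect is modest and does not show that 200 subjects are too few.

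**What to change.** - **Section 1.1.4 and synopsis:** delete *at least* before 42. State which age group the 19% covers. Give the expected number of positives with its range, among subjects with an evaluable CSF result: about 42 (95% range 31 to 54) if 19% is the 65-70 rate, or about 33 to 40 expected, with the age split stated, if it is the pooled 65+ rate.
- **Section 9.6:** define a completer as a subject with a valid CSF Aβ 1-42 result as well as the 4-hour plasma sample. Report the number with a valid CSF result and plasma sample as the denominator of the main analysis.
- **Section 4.2, criterion 3:** reconcile with the synopsis wording.

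The cost is protocol wording and a sample-size statement that is somewhat less favourable. No increase in N is required.

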1.1.5 Study design

Single-centre, observational, correlational study.

1.1.6 Study duration

This study involves a single occasion, which will take place during the day and will not involve overnight stay.

1.1.7 CNS outcome variables

NeuroCart assessments

- Adaptive tracking test;
- Visual Verbal Learning Test (VVLT);
- Milner Maze test;
- Face encoding and recognition test;
- N-back test;

- Sustained Attention to Response test (SART):
- Finger tapping.

Neurophysiological NeuroCart assessments

- 21 leads electroencephalogram (EEG);
- Smooth and saccadic eye movement.

Neuropsychological tests

- Clinical Dementia Rating scale (CDR);
- Instrumental Activities of Daily Living scale (IADL).

Handgrip strength

JAMAR hydraulic hand dynamometer

1.1.8 Biochemical outcome variables

CSF biomarkers

- Aβ concentration (1-40, 1-42 and 1-42/1-40 ratio);
- T-Tau and p-Tau concentrations;
- NfL concentration.

Plasma biomarkers

- Aβ concentration (1-40, 1-42);
- T-Tau and p-Tau concentrations;
- NfL concentration.

Exploratory biomarkers including but not limited to:

- Synaptic loss; Neurogranin [24],
- Glial inflammation; YKL-40 [25],
- Levels of p-Tau181 in extracts of neutrally-derives blood exosomes [26],
- MicroRNAs [MiR-155, MiR-107 and MiR-29 [27]]).

Genetics

APOE ε genotype;

1.1.9 Statistical methodology

Descriptive statistics will be used to summarize the data. Data will be graphically processed for visual inspection.

In order to develop an algorithm that can classify the subjects between ADpath+ and ADpath- there will be a two-step procedure. In the first step 500 bootstrap samples will be generated out of the original data and logistic regression with LASSO penalization (in order to account for the expected small event per variable ratio) in each of the bootstrap samples with all the candidate variables (CNS and biochemical outcome variables, age and educational level) will be performed. Out of all the candidate variables the ones that consistently and most frequently appear in the bootstrap models will be selected. Hence, in this first step the variable selection will take place. In the second step another 500 bootstrap samples will be generated and logistic regression will be performed (with penalization if necessary) in each of the bootstrap samples. This time only the variables that were selected in step 1 will be entered in the model. The estimates out of all the bootstrap models will be averaged and used in order to obtain predictions in the original data. Step two will result in the bootstrap-corrected predictions that will be assessed in terms of calibration (calibration slope), discrimination (c-index) and squared mean prediction error.

To investigate the relationship between biomarkers and gene carriers and NeuroCart scores, correlations and regression analyses will be used.

NeuroCart scores will be analysed with an analysis of variance (ANOVA) and/or multivariate analysis of variance (MANCOVA) to estimate differences between the groups of elderly with different $A\beta$ status.

The intra- and inter-individual diurnal fluctuation will be investigated with mixed-model analysis.

2 STUDY OBJECTIVES

Main objectives:

To define an algorithm based on the plasma biomarkers: A β 40, A β 42, t-Tau, p-Tau, NfL and APOE ϵ status and NeuroCart tests, age, grip strength and level of education that distinguishes between positive and negative A β CSF in healthy elderly.

Exploratory objective:

To determine the correlation between AD-specific biomarkers in CSF (Aβ 1-40 and 1-42, Tau proteins, NfL) and the NeuroCart scores in a cohort of 200 healthy elderly subjects.

To determine the correlation between AD-specific biomarkers in plasma (Aβ 1-40 and 1-42, Tau proteins, NfL) the NeuroCart scores in a cohort of 200 healthy elderly subjects.

To determine the correlation between AD-specific biomarkers in CSF (Aβ 1-40 and 1-42, Tau proteins, NfL) and in plasma in a cohort of 200 healthy elderly subjects.

To determine the correlation between APOE ϵ genotype and the A β /Tau/NfL concentrations in CSF in a cohort of 200 healthy elderly subjects.

To determine the correlation between APOE ϵ genotype and the A β /Tau/NfL concentrations in plasma in a cohort of 200 healthy elderly subjects.

To characterize the cohort of healthy elderly subjects in order to yield norm scores for specific NeuroCart tests in all subjects.

To characterize the plasma biomarkers across multiple times of day to gain understanding of intraand inter-subject variability, and thus diurnal fluctuation.

3 STUDY DESIGN

3.1 Overall study design and plan

The total duration of the study for each subject will be a minimal of 2 days divided as follows:

- Screening: Up to 21 days before study day;
- Study assessments: Day 1.

3.1.1 Screening

Before deciding to participate in this study, subjects will be invited to take part in an information meeting during which all study related procedures will be explained and possible risks will be extensively addressed.

The screening phase will only be started after full written, verbal and signed informed consent has been obtained, according to CHDR standard operating procedures. A medical screening (medical history, physical examination, routine haematology and urinalysis) will be performed to assess a subject's eligibility for this study. This to exclude any comorbid disorders which might influence the study results. Next to the medical screening there will also be a cognitive screening part. Subjects will be screened for significant symptoms of dementia and depression using the MMSE and GDS-15, respectively. The NeuroCart assessments will be practiced following the medical and cognitive screening, to study the subject's capability to perform the NeuroCart tests during the study visit.

3.1.2 Neuropsychological testing period

The time schedule of the study day is provided in the study flow charts Table 1. Subjects will visit CHDR for approximately 4 hours on the study day and will not have to be admitted or stay overnight.

3.1.3 Follow-up

There will be no follow-up visit as no clinical/safety follow-up measurements are needed in this non-interventional, correlational study. The first 20 subjects who have participated in the study will be asked to fill in a visual analogue scale question rating the burden of the study. Also, these 20 subjects will be contacted by telephone 48 hours after the LP was performed to check for adverse events.

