Based on extensive longitudinal biomarker studies [6, 7] a specific pattern of deterioration of AD specific biomarkers has been proposed, which reflects the underlying progressive neuropathology of the disease. In this model, described by Jack et al., (2013) concentrations of A β in CSF start decreasing decades before clinical symptoms appear. Changes in total and phosphorylated tau (t-Tau, p-Tau) concentrations have been shown to occur in CSF up to 15 years prior to the clinical onset of AD [8]. As the disease process progresses, cognitive functions start to decline; at first only noticeable through sophisticated neuropsychological testing, but eventually also clinically evident.

In the clinical setting, the diagnosis of (probable) AD is made based on the clinical picture, combined with neuropsychological testing, and confirmed by evidence of amyloid pathology in CSF (abnormal Aβ and/or Tau levels) or on amyloid PET scans, when available. The collection of CSF is, however, an invasive technique which could result in discomfort with a chance of side-effects (e.g. post-puncture headache) while PET scans are time consuming, not available for all patients, and expensive [9, 10].

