Plasma levels of Aβ40, Aβ42 and NfL, APOE ϵ status and NeuroCart tests of the 200 subjects willing to undergo a lumbar puncture will be used to define an algorithm that will be able to improve the efficiency of finding subjects who have an Aβ positive (CSF) profile. The subjects will be divided in a group yielding subjects who are suspected of AD pathology (ADpath+) by the algorithm and subjects who are suspected to be without AD pathology (ADpath+). To confirm the correct classification potential of the algorithm, the outcome will be compared to the CSF Aβ outcome of the subjects. CSF ADpath+ and a CSF ADpath- defined by an Aβ 1-42 CSF level ≤450 pg/mL for ADpath+ subjects and an Aβ 1-42 CSF level ≥451 pg/mL for ADpath- subjects, will be used to differentiate between the two groups (using the Single Molecule Array assay; Simoa assay [19]).

If the ability of the algorithm to discriminate between subjects who are likely to have a biomarker profile indicative of AD pathology and subjects with a normal biomarker profile is confirmed by evidence of pathology in CSF, it could be decided to not perform lumbar punctures in subjects who are very likely to have a *normal* CSF biomarker profile based on the algorithm in future studies. This will allow for a noninvasive method to pre-select healthy subjects likely to have A β pathology in the CSF and therefore to fewer healthy elderly subjects who will have to undergo a lumbar puncture. The results of this study can also be used for subject selection for research that specifically targets a certain biomarker (e.g NfL).

As an exploratory objective, plasma samples will be analyzed for diurnal fluctuation in this current study. Diurnal fluctuation in the concentration of CSF biomarkers has been reported and may represent a pre-analytical confounding factor in the laboratory diagnosis of AD [20]. Plasma biomarkers for AD have however not been extensively studied for possible fluctuating levels during the day. The results will also provide more information about the effect of the clearance systems of the brain which removes proteins (e.g. $A\beta$) from the brain via various overlapping clearance systems [21]. These clearance systems may be the cause of the diurnal fluctuation reported in CSF. This knowledge can be used in future clinical trials to perform certain assessments (e.g. LP and blood samples) at the most useful time points.

Objective(s)

Main objectives:

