In order to develop an algorithm that can classify the subjects between ADpath+ and ADpath- there will be a two-step procedure. In the first step 500 bootstrap samples will be generated out of the original data and logistic regression with LASSO penalization (in order to account for the expected small event per variable ratio) in each of the bootstrap samples with all the candidate variables (CNS and biochemical outcome variables, age and educational level) will be performed. Out of all the candidate variables the ones that consistently and most frequently appear in the bootstrap models will be selected. Hence, in this first step the variable selection will take place. In the second step another 500 bootstrap samples will be generated and logistic regression will be performed (with penalization if necessary) in each of the bootstrap samples. This time only the variables that were selected in step 1 will be entered in the model. The estimates out of all the bootstrap models will be averaged and used in order to obtain predictions in the original data. Step two will result in the bootstrap-corrected predictions that will be assessed in terms of calibration (calibration slope), discrimination (c-index) and squared mean prediction error.

To investigate the relationship between biomarkers and gene carriers and NeuroCart scores, correlations and regression analyses will be used.

NeuroCart scores will be analysed with an analysis of variance (ANOVA) and/or multivariate analysis of variance (MANCOVA) to estimate differences between the groups of elderly with different $A\beta$ status.

The intra- and inter-individual diurnal fluctuation will be investigated with mixed-model analysis.

Table 1 Visit and Assessment Schedule

	SCR	Study day 1									
Time point Assessment	Up to -21 d	-0.25h	0h	0.5h	1h	1.5h	2h	2.5h	3h	4h	48h
Informed consent	Х										
Demography	Х										
Inclusion and exclusion criteria	Х										
Medical history	X										
Physical examination	Х										
Fundoscopy	X										
Temperature	X										
Height and weight	Х										
Concomitant medication	X	Х									
Virology	X										
BsHaem	X										
UrDrug, BrAlc	Х	X									
General symptoms	X										X ¹
Vital Signs (HR, BP)	X										
Meal/snack	X		Χ								
Geriatric Depression Scale	X										
Mini Mental State Examination	X										
Adaptive tracking test	X ²			X							
Visual Verbal Learning Test (VVLT) immediate	X ²				X						
VVLT delayed	X ²					Χ					

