VVLT recognition	X ²					X					
Milner Maze Test (MMT) immediate	X ²			X							
MMT reversed	X ²			X							
MMT delayed	X ²				X						
Face encoding and recognition test	X ²				X						
N-Back	X ²						Х				
Sustained Attention to Response Test	X ²				X						
Finger tapping	X ²							X			
Electroencephalography (EEG)					X						
Smooth & saccadic eye movements	X ²			Х							
Clinical Dementia Rating scale			Χ								
Instrumental Activities of Daily Living scale			X								

¹ At the end of the study day, the first 20 subjects will rate the burden of the study by answering a Visual Analogue Scale question. These 20 subjects will also be contacted by telephone 48 hours after LP to check for AEs.

² PD tests training session.

JAMAR dynamometry						Χ			
Plasma sample biomarker research			X^3			X		X ⁴	
Blood sample genotyping			Χ						
CSF sampling							X		
Discharge	Х							X	
Con-meds		<>							

_

³ Subjects will be unfed for first plasma biomarker sample due to the influence of fat on the adequate isolation of exosomes from plasma. Subjects will be offered breakfast/lunch thereafter.

⁴ Plasma sample closest to CSF sample (4h sample) will be used to compare CSF and plasma biomarkers.

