4 STUDY POPULATION

4.1 Subject population

A minimum of 200 subjects will be enrolled in the study following satisfactory completion of a screening visit where eligibility for the study will be checked. Males and females will be included from the age of 65 and over. At least a hundred subjects will be above the age of 70. Subjects will be randomised to participate in the morning or afternoon to have an equal time of day distribution.

Subjects will be recruited via media advertisement or from the subjects' database of the Centre for Human Drug Research, Leiden, the Netherlands.

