4.7 Lifestyle restrictions

Approximate meal times will be according to the study schedule. Poppy seed or foods containing poppy seeds are not permitted from 3 days before screening.

Alcohol will not be allowed from at least 24 hours before screening and before the study day. Between screening and the study visit, daily alcohol consumption exceeding 2 standard drinks per day on average for females or exceeding 3 standard drinks per day on average for males will not be permitted (one unit is 10 grams of alcohol). Subjects will undergo an alcohol breath test the morning of the study day.

Subjects will not be allowed to have excessive caffeine consumption, defined as >800 mg per day from 7 days prior to the study day. Subjects will abstain from caffeine-containing products for 24 hours prior to the start of the screening and study day. Caffeine quantities defined as: one cup of coffee contains 100 mg of caffeine; one cup of tea, or one glass of cola, or potion of chocolate (dark:100 g, milk 200 g) contains approximately 40 mg of caffeine; one bottle of Red Bull contains approximately 80 mg of caffeine.

Strenuous physical activity (e.g., heavy lifting, weight or fitness training) is not allowed from 48 hours prior to the screening. Light ambulatory activities (e.g. walking at normal pace) will be permitted.

Subjects are asked not to use NSAIDs (e.g. ibuprofen, diclofenac) in the ten days prior to the study day till one day after the study day (LP).

Subjects will be required to fast 4 hours before the start of the study occasion. Water is allowed as required. Subject will only have to fast for the first blood sample on the study day and will be offered breakfast/lunch thereafter.

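### The only adverse-event enquiry scheduled after discharge from the lumbar puncture covers the first 20 of at least 200 subjects

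*Protocol*

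**What the plan says.** Section 4.1 sets the size: "A minimum of 200 subjects will be enrolled in the study". The synopsis (Background & Rationale) makes the puncture part of the study for all of them: "NeuroCart tests of the 200 subjects willing to undergo a lumbar puncture will be used to define an algorithm". CSF Aβ is the reference against which the algorithm is judged (section 4.4). Section 1.1.1 says that CSF sampling "may lead to side effects, for instance post-dural puncture headache or bruising".

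Subjects attend for about four hours and do not stay overnight (section 3.1.2). Section 3.1.3 plans no follow-up visit. It asks the first 20 subjects to rate the burden of the study, and adds that "these 20 subjects will be contacted by telephone 48 hours after the LP was performed to check for adverse events". Footnote 1 to Table 1 agrees: "These 20 subjects will also be contacted by telephone 48 hours after LP to check for AEs".

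Table 1 has no adverse-event row. The nearest is "General symptoms", which is marked at screening and at 48 h, and the 48 h mark carries footnote 1. Section 9.7.4 will summarise numbers of events and of subjects with events by MedDRA class and term, and list all events.

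**The concern.** The protocol anticipates a harm from a procedure given to everyone. It has a simple way of asking about that harm two days later, and it applies this to a small leading block of subjects. From subject 21 onward, nothing in Table 1, section 3.1.3 or section 8 schedules a question about adverse events once the subject has gone home.

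Two things are at stake. One is subject care: a subject with a headache after discharge is asked about it only if among the first 20. The other is how to read the section 9.7.4 counts. They combine two kinds of ascertainment, active questioning and spontaneous report, and the protocol does not separate them. A low count could mean few events or few reports.

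**Working it through.** **Is there any other scheduled enquiry after the puncture?** Taking each candidate in turn:

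- Table 1, symptoms row: screening precedes the puncture, and the 48 h mark is limited to the first 20.
- Section 7.1.3 requires findings that qualify as adverse events after the start of participation to be recorded, with no limit to 20. It sits under physical examination, which is done at screening, and it schedules no later enquiry.
- Section 7.1.4 (CSF sampling) provides treatment for post-dural headache in any subject, once the headache is known.
- Section 8.1.6 requires events to be followed to resolution or stability, again once known.
- Section 8.1.5 sets reporting times for serious events in all subjects, counted from first knowledge.

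None of these is a scheduled question to subjects 21 onward.

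**Coverage.** Inputs: 20 called (section 3.1.3; Table 1, footnote 1) and at least 200 enrolled (section 4.1).

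- Called: 20/200 = 10%. This is a maximum, because 200 is a minimum.
- Not called: 200 − 20 = 180, or 180/200 = 90%. Both are minimums.
- If every subject were called: 200/200 = 100%, which is 180 more calls at an enrolment of 200.

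**Can the under-count be sized?** Suppose the event rate is the same in both groups and a call finds every event present by 48 hours. Let *s* be the share of such events that uncalled subjects report unprompted. The fraction of all events that is recorded is then

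(20 + 180·*s*)/200 = 0.10 + 0.90·*s*

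At *s* = 1 this is 1.00, so there is no under-count. At *s* = 0 it is 0.10, an arithmetical floor and not a forecast. The protocol gives neither an event rate nor any basis for *s*, so the size cannot be computed. Zero lies within the range.

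**The case against.** The strongest reply is that this is a choice and not a mistake. Section 3.1.3 and Table 1 agree, and giving the same 20 subjects both the burden question and the call looks like a deliberate early check. Risk is reduced by a 25G atraumatic needle, neurologist supervision, exclusion of subjects with contraindications and an information meeting about risks. Headache is symptomatic, so a subject can report it unprompted. What subjects were told to report would normally be in the consent pages and standard operating procedures, which are not shown. The synopsis lists safety endpoints as not applicable, and section 9.7.4 is descriptive only.

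Much of this stands. There is no contradiction, no planned inference is damaged, and the consequence may be small. It does not supply the missing enquiry. The protocol does not call the 20 a pilot, and no rule links their answers to stopping or extending the calls. The protocol also still defines, follows and tabulates adverse events.

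A reader might infer more than the text supports:

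- *That the protocol's own reason fails.* Section 3.1.3 cites the non-interventional design to explain why there is no follow-up visit. It does not offer this as the reason for stopping the calls at 20, so there is no stated reason to rebut.
- *That the NSAID restriction shows a call was owed.* Section 4.7 restricts NSAIDs until the day after the puncture. That is an instruction to the subject and needs no contact.
- *That 20 calls are too few for the halting judgement in section 8.2.* No event in 20 calls leaves rates up to 1 − 0.05^(1/20) = 13.9% compatible (one-sided 95%), against 1 − 0.05^(1/200) = 1.5% for 200 calls. But section 8.2 responds to anything that occurs, from any source. Nothing ties it to these calls, and no harm rate is to be estimated.

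**Conclusion.** The point holds as a gap in scheduled ascertainment. At most 10% of subjects have an adverse-event enquiry after discharge, and for 180 or more none is scheduled. Delayed non-serious events in that group depend on spontaneous report, and the section 9.7.4 counts mix the two kinds of ascertainment.

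This rests on two readings: that every enrolled subject has the puncture, as the plan intends, and that no unseen procedure adds a routine contact. The scheduling fact is clear from the text; the effect on the counts is not. A reader might conclude that events are being missed, but the protocol supports only that they could be, by an unknown amount that may be zero. The algorithm objective and serious adverse event reporting are unaffected. The point is therefore a worthwhile, inexpensive improvement to subject care and to the adverse-event record, and does not correct an error in the analysis.

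**What to change.** In section 3.1.3 and in footnote 1 to Table 1, state that every subject who has a lumbar puncture is telephoned 48 hours later and asked about adverse events. Keep the burden question for the first 20. As a consequence, redefine the end of study in section 10.7 as the last subject's 48-hour call in place of the 200th study visit, which moves it by two days.

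The cost is about 180 short calls using a procedure already planned for 20 subjects, with no new visit or invasive procedure. The protocol gives no staffing figures, so the assumption that existing staff can absorb the calls is the sponsor's to confirm. A change in study procedures is a substantial amendment under section 10.6.2 and needs ethics committee approval and the competent authority's notification of no objection. One call at 48 hours will still miss events that begin later, but all subjects would then be asked in the same way.
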